6.2. Adverse Events

Adverse events summaries will only consider treatment emergent adverse events (TEAEs). TEAEs are defined as those adverse events that occurred after dosing and those existing adverse events that worsened during the study based on the start date and time. If it cannot be determined whether the adverse event is treatment emergent due to an incomplete (partial) onset date, the adverse event will be considered treatment emergent. AEs will be recorded from the time of first dose of IMP until Follow-up (Visit 17).

Verbatim terms entered into the clinical database via the EDC system will be mapped to preferred terms and system organ classes using version 25.1 of Medical Dictionary for Regulatory Activities (MedDRA).

Summaries that are displayed by system organ class and preferred terms will be ordered by descending order of incidence of system organ class and preferred term within each system organ class. Adverse event summaries of the following types will be presented for the Safety Population:

- Overall summary of the TEAEs which contain an overview of each item below.
- Subject count and incidence rate of TEAEs and total number of unique TEAEs by MedDRA system organ class and preferred term.
- Incidence rate of TEAEs by MedDRA preferred term and highest severity. Severity is defined by three categories: "Mild", "Moderate", and "Severe." At each level of subject summarization, a subject is classified according to the highest severity if the subject reported one or more events. Adverse events with missing severity will be considered severe for this summary.
- Subject count and incidence rate of TEAEs by MedDRA preferred term and
 closest relationship to study drug (Related/Not Related). At each level of subject
 summarization, a subject is classified according to the closest relationship if the
 subject reported one or more events. Adverse events with missing relationship
 will be considered related for this summary.
- Subject count and incidence rate of Serious TEAEs by MedDRA system organ class and preferred term.
- Subject count and incidence rate of TEAEs leading to withdrawal of study medication by MedDRA system organ class and preferred term.
- Subject count and incidence rate of TEAEs leading to dose modification (defined as dose increased, dose reduced, dose interrupted on the CRF) by MedDRA system organ class and preferred term.
- Subject count and incidence of TEAEs leading to death as an outcome by MedDRA system organ class and preferred term.
- Subject count and incidence rate of TEAEs of special interest (defined as any renal event as indicated on the AE CRF, and all other AESI (ophthalmological, cardiac, and liver function) will be determined by a clinical review of MedDRA coded terms prior to database lock) by MedDRA system organ class and preferred term.

6.3. Clinical Laboratory Evaluations

Blood and stool samples will be collected at Visit 1 (Screening), Visit 3 (Baseline), and Visit 13 (End of Treatment) or upon early termination for analysis of biomarkers and gut

microbiome. Biomarkers and gut microbiome analysis will be described in a separate analysis plan.

Blood and urine samples will be collected at all except Visit 2 for screening and safety. Laboratory parameters (chemistry, hematology, urinalysis) will be presented in data listings. Abnormal values will be flagged as high or low relative to normal ranges, where applicable, by the laboratory vendor.

Change from baseline in numeric laboratory parameter values will be summarized using descriptive statistics at all visits.

For those laboratory tests in which normal ranges are available, shifts from baseline will be presented. Categories for the shift tables will be low, normal and high.

Laboratory parameters will be classified according to the categories given by the laboratory vendor. The laboratory categories from the vendor listed below will be assigned to the following categories for data summaries.

Chemistry	Hematology	Urinalysis
Amphetamines Conf	PT/INR/APTT	Microalbumin, UR Random
Bun/Creatinine Ratio		
EGFR (Bedside Schwartz)		Urine Chemistry
Hemoglobin A1C		
Pregnancy, qualitative		
Thyroxine, Free		
Triiodothyronine, Free		
TSH Ultrasensitive		
Urine Drug Screen w/ Con		

6.4. Physical and Neurological Examination

A physical examination will be conducted at all in-clinic visits. The procedure will include the following organ systems: Head, ears, eyes, nose, and throat; Skin; Cardiovascular; Respiratory; Gastrointestinal; Genitourinary (as appropriate or indicated); Musculoskeletal; and Allergies. The exam will include an assessment for sign of bladder or kidney pathology including an exam of the abdomen and both flanks.

Assessment of edema will also be done. Exam may include suprapubic exam (bladder palpation) if decreased urine output is noted.

A neurological examination will also be conducted at all in-clinic visits. A standard neurological exam will be conducted to include an evaluation of mental status, cranial nerves, motor exam, sensory exam, cerebellar (coordination, gait), and reflexes.

[figure not shown]
A modified version of the physical and neurological exams will be done by a physician via telemedicine at the remote visits. As part of the in-home visit, the nurse will conduct a targeted physical exam including assessment of general appearance, an abdominal and a costovertebral angle tenderness exam, assessment for signs of cystitis, and an assessment of edema. Exam may include suprapubic exam for bladder palpation if decreased urine output is noted.

All examination results will be reported as normal or abnormal. Clinical significance will

The results of all examinations will be presented in data listings.

6.5. Ophthalmology Assessment

be determined for abnormal results.

The results will be presented in data listings.

6.6. Vital Signs

Weight, systolic blood pressure (SBP; in mmHg), diastolic blood pressure (DBP; in mmHg), heart rate (bpm), respiratory rate (rpm), and body temperature (°C) will be collected at the Screening visits (Visit 1 and 2) and all post-baseline study visits. Vital signs will be taken after the subject has been seated for 5 minutes. The initial blood

pressure reading will be summarized in the table. Height will be measured at the Screening visit (Visit 1), Baseline (Visit 3), and End of Treatment (Week 13, Visit 16).

Summary statistics for each measurement and the change from baseline will be presented at each post-baseline visit. All vital sign measurements will be presented in data listings. A separate table and listing will be provided for blood pressure.

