5.6 Preclinical Data

5.6.1 Overview of Pharmacology and Toxicology Findings

A battery of safety pharmacology and toxicology studies conducted *in vitro* and *in vivo* in mice, rats and dogs has been conducted, providing safety support for the progression of the drug Phase 2 clinical trials. The nonclinical safety studies suggest that NNZ-2591 is unlikely to have adverse effects in human subjects in the cardiovascular system, nervous system, or respiratory system, nor in skeletal, motor, or reproductive function. NNZ-2591 has been tolerated in repeat-dose toxicology studies at doses up to 2000 mg/kg/day in juvenile rats and 400 mg/kg/day in adult dogs for 14 days and up to 400 mg/kg/day in juvenile rats and 120 mg/kg/day in adult dogs for 13 weeks.

Studies of NNZ-2591 in juvenile animals have demonstrated a favorable safety profile.

In the 14-day study in adult dogs as well as the 13-week studies in adult dogs and juvenile rats, there was a decrease in body weight and food consumption in high dose animals that resolved during the 4-week recovery period. High dose dogs showed an increase in abnormal feces which again resolved during the recovery period.

In vitro metabolism studies have shown NNZ-2591 to be highly stable to metabolism in human hepatic microsomes, hepatocytes and human plasma. NNZ-2591 has also been shown not to be significantly metabolized by human CYP450 enzymes. *In vivo* studies in rats have shown NNZ-2591 to be excreted primarily (>99%) via the kidney with less than 0.3% in bile and feces. These results confirm that metabolism is not a significant route of elimination.

Neuren Pharmaceuticals Ltd.	Clinical Trial Protocol	Version 3.0
Confidential	Neu-2591-PMS-001	October 30, 2023

In vitro cell permeability and *in vivo* PK studies have shown NNZ-2591 to be approximately 100% orally bioavailable, and NNZ-2591 has demonstrated the ability to cross the blood brain barrier.

Summaries of these studies are presented in the NNZ-2591 Investigator's Brochure.

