If the manual blood pressure measurements suggest increased blood pressure, an additional blood pressure measurement should be performed manually later in the same visit. If there is a change in blood pressure from baseline, a repeat measurement should performed manually later in the same visit. The clinician should also document any factors that may affect the blood pressure measurements such as the subject's state (e.g. excited, agitated), hydration level, if the measurements could not be taken seated, or if the subject was uncooperative. If blood pressure measurements suggest elevation, the Investigator should also conduct a medical review with physical exam, and review safety labs, in particular, serum creatinine, urinalysis, and urine volume. If after at least 2 measurements have been taken at the visit, there is confirmed clinical suspicion of true elevation of blood pressure, or if the subject is agitated or uncooperative and the blood pressure cannot be confirmed, or there is a change in blood pressure from baseline, blood pressure should be re-assessed again within 12-24 hours. If elevated blood pressure is confirmed and meets the stopping criteria below, dosing should be discontinued, and a referral should be made to the child's primary care pediatrician or a kidney specialist as deemed appropriate by the Investigator and the Medical Monitor.

IMP must be discontinued at any time during the study in the event that any of the following values are observed on blood pressure exams based upon repeated testing on at least three visits.

- For children ages 3-12 years: \geq 95th percentile (based on height) + 12 mmHg OR \geq 140/90 mmHg
- For adolescents ages 13 years and above: \geq 140/90 mmHg (in case a 12-year-old turns 13 years old during the study)

These must be reported and discussed with the Medical Monitor.

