For simulation of exposure for children 3-17 (covering the planned age group for this Phase 2 study and studies in PTHS and AS with children up to 17 years old), the Centers for Disease Control and Prevention (CDC) Growth Individual charts with 3rd and 97th percentiles (3rd, 10th, 25th, 50th, 75th, 90th, and 97th) were downloaded from the CDC.gov website. The body weights for boys and girls from 36.5 months (3 years) to 17 years old (203.5 months) inclusive were combined for the input to Phoenix WinNonLin as a csv file. The file contained columns for 3rd, 5th, 10th, 25th, 50th, 75th, 90th, 95th, and 97th percentiles for each month of age and gender individually. Column with gender was added for the combined dataset. Age groupings for the allometric scaling analysis were Group 1 (3 to < 6), Group 2 (6 to <12), and 12-17.

The equation for allometric scaling was implemented in the Data Wizard function of Phoenix WinNonLin using weight for children of different age, gender, and percentile as direct input.

Doses were varied in the range from 11 to 20 mg/kg for final estimate with 1 mg/kg increments. The dose levels 11, 12, 13, 14, \dots 20 mg/kg were used to calculate the related exposures for different body weight values and compare the resulting AUC_{tau} values with adult results.

Additionally, a 17.5-mg/kg dose was evaluated for the lowest body weights. Preliminary evaluation of suitable doses was done starting from 3 mg/kg dose levels. The parameters derived for this allometric scaling were AUC_{tau} at steady state to compare with adult exposures.
2. Allometric Scaling Results

Non-compartmental parameters for NNZ-2591 in adult subjects from the study Neu-2591-HV-001 were evaluated for dose proportionality of exposure after single, first doses and multiple steady-state doses of NNZ-2591 in healthy adult subjects. Evaluation of dose proportionality supported the application of the published allometric scaling formula to steady state exposure parameter AUC_{tau} to be matched to adult exposures using body weight normalized dose in mg/kg and apparent steady state clearance in healthy adult subjects. The predicted exposures (steady-state AUC_{tau}) were calculated from adult median CLss/F, estimated for morning and evening 12 mg/kg doses on Day 7 in the study Neu-2591-HV-001, for different dose values and body weights from CDC Growth Chart.

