An independent DSMC will monitor the progress of the trial and ensure that the safety of trial subjects is not compromised. The DSMC will review the clinical safety data prior to any individual dose titration and prior to initiation of subsequent age groups. The DSMC will review safety data and make a determination regarding 1) the ability for any individual subject to escalate to the next higher dose and 2) the ability for enrollment to begin in the younger age groups (Groups 2 and 3). The DSMC will consist minimally of a clinical chair, another physician experienced in clinical trials with pediatric expertise (but not participating in this study), and a pediatric cardiologist. The DSMC Charter details the DSMC processes, duties, and responsibilities as well as the study-wide stopping criteria.

Data for the DSMC is provided as raw data listings for up-titration decisions and opening of enrollment in Groups 2 and 3, as specified in the DSMC Charter. Overall safety reviews are also conducted as defined in the DSMC charter and data is provided as SAS listings. Additional summary analyses may be done as requested. There is no separate Statistical Analysis Plan for the DSMC.

4. Statistical Methods

The statistical analyses will be reported using summary tables, listings, and figures (TLFs). Numbering for TLFs will be based on the recommended numbering convention provided by the International Conference on Harmonization. Both prespecified and *a posteriori* exploratory analyses will be conducted consistent with the exploratory design of the study. Unless noted otherwise, all statistical tests will be two-sided with a nominal significance level of $\alpha = 0.05$. Continuous variables will be summarized with means, standard deviations, medians, minimums, and maximums. Categorical variables will be summarized by counts and percent of subjects in corresponding categories. Missing values are not considered for percent calculations, unless stated otherwise. Footnotes will be used to specify the percent calculation when applicable. Baseline is defined in Section 4.3 for efficacy and safety parameters.

Individual subject data obtained via the electronic data capture (EDC) system and from external vendors will be presented in listings.

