4.3. Definitions

- The baseline measurement for an efficacy variable will be based on the average values of visits 1-3 for assessments collected at more than one visit. For assessments collected once during the Screening/Baseline period, the most recent non-missing assessment will be used. For safety assessments, value at Visit 3 (Baseline) or the most recent non-missing assessment will be used.
- Age will be derived as the integer value of informed consent/assent date minus birth date plus one, then divided by 365.25.
- The age at time of assessment in calculated as (date of assessment date of birth + 1)/365.25.
- Body Mass Index (BMI) will be derived as weight in kilograms divided by height in meters squared.
- The change from baseline measurement for a variable at a particular visit will be derived as the measurement taken at the specified visit minus the baseline measurement. CGI-I will not have a change from baseline measurement; the within-subject treatment change is assessed by the value at the End of Treatment Visit.
- Treatment duration in days will be derived as follows: Date of Last Dose Date of First Dose + 1.
- Study duration will be defined as the total number of days in the study (date of last visit date of informed consent + 1).
- History of developmental regression will be determined from the medical history question as reported on the PMS diagnosis page of the CRF: "Has the child undergone a regression of skills in the past?" If coded as "yes" the subject is considered as having had a past developmental regression.
- Autism Spectrum Disorder (ASD) diagnosis will be derived from the PMS diagnosis page of the CRF. If ASD is checked to the under "confirmation of psychiatric co-morbidities", the subject is considered as having the disorder-
- Bipolar Disorder will be derived from the PMS diagnosis page on the Case Report Form (CRF). If "Bipolar disorders" is checked to the under "confirmation of psychiatric co-morbidities", the subject is considered as having the disorder.

- Attention Deficit Disorder will be derived from the PMS diagnosis page on the CRF. If "Attention Deficit Disorder" is checked to the under "confirmation of psychiatric co-morbidities", the subject is considered as having the disorder.

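### SAP 6.6 summarises weight only as observed values and raw change, which in a single-arm study of growing children can mask slowed weight gain

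*SAP*

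**What the plan says.** SAP 6.6 covers weight together with blood pressure, heart rate, respiratory rate and temperature. The planned output is: "Summary statistics for each measurement and the change from baseline will be presented at each post-baseline visit". By-subject display is also planned: "All vital sign measurements will be presented in data listings".

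SAP 4.3 defines change from baseline as "derived as the measurement taken at the specified visit minus the baseline measurement". SAP Section 4 fixes the statistics: "Continuous variables will be summarized with means, standard deviations, medians, minimums, and maximums". BMI is listed only as a baseline characteristic (SAP 5.3). Neither document plans a weight-for-age z-score or percentile, a percent change in weight, or a count of children by size of weight change.

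Two other parts of the protocol bear on this. Section 5.6.1 reports that in the 14-day dog study and the 13-week dog and juvenile-rat studies "there was a decrease in body weight and food consumption in high dose animals that resolved during the 4-week recovery period". Appendix A shows that the sponsor has already worked with a growth reference, using "the Centers for Disease Control and Prevention (CDC) Growth Individual charts with 3rd and 97th percentiles" by month of age and sex for the allometric scaling.

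**The concern.** A raw change in weight has a natural zero in adults. In children it does not, because growth alone moves the expected value above zero. With a control arm, growth would cancel in the comparison. Here there is none, so the reader of the weight table has to supply the expected gain from memory, across an age range over which it varies.

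The other safety summaries carry a frame of reference: laboratory values have shift tables against normal ranges (SAP 6.3) and ECGs have shifts in interpretation (SAP 6.7). Weight has none, although vital signs are part of the primary safety endpoint (Protocol 6.3.1.1) and body weight is one of the effects that toxicology reported. At stake is a safety table that could show a flat or slightly positive mean when the children as a group gained less than expected.

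**Working it through.** The plan states no figure for weight change, so there is none to reproduce. The calculation below is an illustration.

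**Inputs**
- Treatment duration: 91 days (Protocol 9.4.2), i.e. 91/365.25 = 0.249 year.
- Sample: about 20 children aged 3 to 12 years, one arm (SAP 1.2).
- Minimum entry weight: 12 kg (Protocol 8.1). The weights of 20 and 40 kg are illustrative.
- Unit: SAP 6.6 gives none for weight; kg is inferred from the BMI definition in SAP 4.3.
- Normal gain: **assumed** 1.5 to 4 kg a year.

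**Step 1. Expected gain without any drug effect** = annual rate × 0.249.
- 1.5 × 0.249 = 0.37 kg; 4 × 0.249 = 1.00 kg.

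| Body weight | Expected gain as % of weight |
|---|---|
| 12 kg | 3.1 to 8.3 |
| 20 kg | 1.9 to 5.0 |
| 40 kg | 0.9 to 2.5 |

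**Step 2. Uniform shortfall.** If every child failed to gain by the full expected amount, each change would be 0 kg. Mean, median and minimum would all be zero, and the listings would look flat. If gain were halved, the mean change would be +0.19 to +0.50 kg (0.37/2 to 1.00/2) and would read as growth.

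**Step 3. Loss in a few children.** Let 4 of 20 children weighing 20 kg each lose 5% (1.0 kg) and the other 16 grow as expected. Mean change = (16 × gain − 4 × 1.0)/20.
- At 0.37 kg: (5.98 − 4)/20 = +0.10 kg, using the unrounded gain of 0.3737 kg.
- At 1.00 kg: (16 − 4)/20 = +0.60 kg.

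The mean stays positive, but the tabulated minimum is −1.0 kg and the listings show all four children.

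**Step 4. Pooling kilograms.** A change of 1 kg is 1/12 = 8.3% at the entry minimum and 1/40 = 2.5% at 40 kg. The raw mean treats the two alike.

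**Step 5. Blood pressure, same reasoning.** On an assumed rise of 0.5 to 3 mmHg a year (also not in the documents), the drift over 91 days is 0.12 to 0.75 mmHg.

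**The case against.** The strongest reply is that weight is watched closely by other routes. It is measured at every visit and listed by child, and with about 20 children the listings can be read individually. Vital-sign changes that the investigator judges clinically significant become adverse events if they meet the definition (Protocol 10.5). Caregivers record changes in oral intake daily (Protocol 9.5.10), the DSMC sees raw listings before each up-titration (SAP Section 3), and further plots are allowed (SAP Section 6). This answers one thing a reader might infer, that growth hides weight loss: Step 3 shows that it does not hide an individual child's loss. It does not answer the point about slowed gain, because none of these routes standardises for growth. Weight is also not among the adverse events of special interest (SAP 6.2), and the extra plots are optional.

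A second reply is that the growth rate is assumed and is for typically developing children. Protocol 5.1 describes feeding problems and cyclic vomiting in this syndrome, so zero gain is not proven to be a drug effect or even a departure from usual. That stands. It limits how a shortfall would be interpreted, but is no reason to leave it out of the table.

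A third is that the toxicology finding was confined to high-dose animals and reversed. That also stands: it makes weight relevant without predicting an effect at the trial doses.

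A reader might extend the argument to blood pressure, since the stopping criterion for ages 3 to 12 contains a percentile, "95th percentile (based on height) + 12 mmHg OR". The documents do not support this. Growth moves blood pressure by less than 1 mmHg in Step 5. The criterion also has an absolute limit of 140/90 mmHg as an alternative and requires repeated testing on at least three visits (Protocol 9.5.1), so converting single-visit readings to percentiles would not reproduce it.

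**Conclusion.** The point holds for weight, in a limited form. The planned summaries cannot separate normal growth from slowed growth. A group shortfall of roughly 0.4 to 1.0 kg over the treatment period, about 2 to 5% of body weight at 20 kg, would be tabulated as zero change, and a smaller shortfall as a gain. The size rests entirely on the assumed 1.5 to 4 kg a year; the direction rests only on children gaining weight over 13 weeks and on the absence of a control arm.

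It would be wrong to conclude that weight loss goes unseen, that animal data predict loss at the trial doses, or that blood pressure needs the same treatment. This is a worthwhile improvement to a primary safety summary, not a flaw that undermines the study.

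**What to change.** In SAP 6.6, keep the raw weight summaries and add, at each post-baseline visit:
- change from baseline in weight-for-age-and-sex z-score on the CDC weight charts, using the age at assessment already defined in SAP 4.3;
- percent change from baseline in weight;
- a descriptive count of children by category of percent change. The documents give no cut-offs, so the categories should be written into the SAP before database lock and labelled as descriptive.

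BMI-for-age z-score at Visits 3 and 16, where height is measured, is optional. It needs a reference that Appendix A does not mention, since that appendix describes body-weight charts only.

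The cost is a few derived variables and table rows from age, sex and weight already collected. Two cautions belong in the text. The Appendix A file is described as percentile columns, so the z-score derivation has to be specified, including for children beyond the outer percentiles. And a general-population reference in a syndromic population means that the change from each child's own baseline should be read, not the absolute z-score, and even that descriptively. No change to the blood pressure summary is asked for under this point.
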